October 4, 2019

Study Title: Cervical Pessary to Prevent Preterm Birth in Singleton Pregnancies With a Sonographically Measured Short Cervix

FDA IDE G140219  
NCT02357394

This study was an open label, randomized controlled trial which was designed to determine if the use of the Arabin cervical pessary would reduce the incidence of preterm birth. At the time of conception, our study differed from other studies regarding the Arabin cervical pessary in that we allowed the use of vaginal progesterone and/or cervical cerclage in the control group. In essence, our study compared the community care standard of practice in our area with the use of the Arabin cervical pessary for an ultrasound diagnosed short cervix.

Our study required an FDA IDE application, assigned number G140219, and registration on clinicaltrials.gov as NCT02357394. Our first patient was enrolled 7/1/2015. Our last patient was enrolled 7/4/2016. Our last data entry occurred in November 2016. We subsequently were unable to enroll any further patients due to low interest. We decided to close the study formally 4/4/2019.

Results were entered to clinicaltrials.gov on 10/4/2019. Due to low number of enrolled subjects (n=7), only raw data is reported. No statistical tests were run.

Signed,

[name] MD  
Assistant Professor  
MFM/OBGYN  
The University of Kansas Health System

**LIST OF ABBREVIATIONS**

AE	adverse event
CFR	Code of Federal Regulations
CRF	case report form
DMC	Data Monitoring Committee
DSMB	Data Safety Monitoring Board
FDA	Food and Drug Administration
GCP	Good Clinical Practice
HIPAA	Health Insurance Portability and Accountability Act of 1996
HSC	Human Subjects Committee, KUMC Local IRB
ICF	informed consent form
ICH	International Conference on Harmonisation
IEC	Independent Ethics Committee
IRB	Institutional Review Board
QC	Quality Control
PI	Principal Investigator
UADE	unanticipated adverse device effect

**PROTOCOL SYNOPSIS**

TITLE	Cervical pessary to prevent preterm birth in singleton pregnancies with a sonographically measured short cervix: an open-label randomized controlled trial
SPONSOR	[name]
FUNDING ORGANIZATION	Unfunded
NUMBER OF SITES	1; University of Kansas Medical Center 2. Medical University of South Carolina
RATIONALE	The Arabin cervical pessary has emerged as a promising treatment for cervical insufficiency. A recent Spanish RCT demonstrated reduced preterm births with the use of the Arabin pessary. The results of this study pessary should also be confirmed here in the USA.
STUDY DESIGN	Open-label, randomized, controlled trial
PRIMARY OBJECTIVE	To determine if the Arabin pessary can reduce preterm birth before 37 weeks in patients with a short cervix
SECONDARY OBJECTIVES	To determine if the Arabin pessary can reduce maternal and neonatal morbidity
NUMBER OF SUBJECTS	256
SUBJECT SELECTION CRITERIA	
Inclusion Criteria:
 
 
• singleton pregnancy
 
• age 18 – 45y
 
• cervical length < 25 mm measured by transvaginal ultrasound prior to 23 weeks 0 days
 
• Agrees to refrain from sexual intercourse
 
 
Exclusion Criteria:
 
 
• major fetal anomalies
 
• painful regular uterine contractions
 
• active vaginal bleeding
 
• ruptured membranes
 
• evidence of chorioamnionitis or other maternal/fetal infectious morbidity
 
• placenta previa
 
• current progesterone therapy
 
• cervical cerclage in situ
 
• visual cervical dilation of 2 cm or greater with visible amnion/chorion
 
• significant maternal-fetal complications (insulin dependent diabetes mellitus, systemic lupus erythematosus with nephritis, chronic hypertension, red cell alloimmunization, drug abuse)
 

INVESTIGATIONAL DEVICE / INTENDED USE	Device: Arabin pessary The intended use is to treat women with cervical insufficiency characterized by a cervix that is too short for gestation as objectively measured on transvaginal ultrasound.

CONTROL GROUP OR OTHER STUDY ARMS (if applicable)	Device: None Patients randomized to the control group will receive standard of care for their condition.
Duration of Subject Participation and Estimated Total Length of Study	Subjects' participation in the study will last about 7 months.  Based on the number of patients KUMC and MUSC examine in a year for cervical length screening in the 2 nd trimester, the study will take 4 years to complete with 80% accrual. We expect a loss to follow up rate of 5%.
PRIMARY ENDPOINT	
 
• Preterm birth less than 37 weeks 0 days gestation
 

SECONDARY ENDPOINTS	
 
• Neonatal composite morbidity – fetal or neonatal death, respiratory distress syndrome (RDS), chronic lung disease, periventricular lucency, periventricular leukomalacia, intraventricular hemorrhage grade 3 or 4, necrotizing enterocolitis, early-onset-culture-proven sepsis
 
• Neonatal length of stay
 
• Neonatal NICU admission
 
• Total NICU days
 
• Duration of ventilator support
 
• retinopathy of prematurity (ROP) requiring treatment
 
• birthweight < 1500g and < 2500g
 
• preterm birth < 34 weeks
 
• gestational age at delivery
 
• use of tocolysis
 
• use of antenatal steroids
 
• chorioamnionitis
 
• vaginal bleeding
 
• preterm premature rupture of membranes
 
• cesarean delivery
 

OTHER EVALUATIONS	Maternal age, body mass index, obstetric history, smoking history, gestational age at randomization, cervical length at randomization, sludge at randomization
SAFETY EVALUATIONS	Patients randomized to the pessary group will be examined for vaginal and cervical infections. Any found infections are treated, and pessary insertion is delayed a week. After insertion, patients are examined for urinary retention. If found, a smaller pessary is inserted. Patients are seen in clinic every 2 weeks, vaginal swabs are examined if symptoms of infection are present, and a questionnaire about symptoms is completed. Pessaries are removed if there is active vaginal bleeding, risk of preterm labor with persistent contractions, or severe patient discomfort.
PLANNED INTERIM ANALYSES	The data will be reviewed every 6 months by the designated medical monitor for the study, [name] MD (neonatologist). The medical monitor is specifically chosen outside of the department of OBGYN to allow for objectivity. Adverse events which would requires immediate suspension of study for review would include an excess of 1 maternal death, 1 maternal ICU admission for sepsis, or 2 perinatal deaths in the pessary group. Unanticipated adverse events will be reported immediately to the Human Subjects Committee (HSC) and the FDA, and its recommendations for temporary cessation or continuation of the study will be followed. If an excess of 4 perinatal deaths occur in the pessary group, the study should be concluded.

STATISTICS Primary Analysis Plan	
The Research hypothesis is that proportion of preterm deliveries before 37 weeks 0 days gestation is reduced in the pessary group as compared to the control group. The primary endpoint and the categorical outcomes that are part of the secondary endpoints will be reported using frequency counts and proportions. For the secondary endpoints that are continuous variables, summary statistics such as mean and standard deviation, or median and inter-quartile range will be reported based on whether the assumption of normality is justified. A chi-square test (or a Fisher's exact test) will be used to perform statistical comparison of proportions across the two groups. Likewise, comparisons for continuous outcomes will be done using a two-sample t-test (or Wilcoxon Rank Sum test) as will be deemed necessary. For gestational age, we will also compare the Kaplan Meier survival curves of the two groups (control and pessary) using the logrank test. Level of significance for all statistical tests will be set at 0.05.

Rationale for Number of Subjects	
Based on KUMC and MUSC hospital data, the proportion of preterm births before 37 weeks 0 days gestation in patients with short cervixes is 30%. In order to detect a reduction in half to 15%, a sample size of 242 will be required to have power of 80% using a two-sided z-test assuming pooled variances. Level of significance is set at 0.05. We anticipate a loss to follow up rate of 5%. We expect to enroll 256 subjects.

## 1.0 PURPOSE OF THE INVESTIGATION

### 1.1 Name of investigational device

Device Name: Arabin pessary

Company/Manufacturer: [name] & Co. KG

Address: [name]

### 1.2 Intended use of the investigational device

The intended use is to treat women with cervical insufficiency characterized by a cervix that is too short for gestation as objectively measured on transvaginal ultrasound.

### 1.3 Report of Prior Investigations

#### 1.3.1 General

*The report of prior investigations shall include reports of all prior clinical, animal, and laboratory testing of the device and shall be comprehensive and adequate to justify the proposed investigation.*

The Arabin pessary was first described clinically for the treatment of cervical insufficiency in a 1990 article published in German (6). Although good outcomes were obtained, it would be 13 more years before another study reintroduced the Arabin pessary for the treatment of cervical insufficiency (2). This 2003 pilot project consisting of 46 at risk patients again demonstrated improved outcomes characterized by a 32 day prolongation of gestation in singletons and an 18 day prolongation of gestation in twins compared to patients without pessary. The authors acknowledged a larger RCT needed to be done. In 2012, a large RCT including 385 singleton pregnancies was concluded demonstrating the Arabin pessary prolonged pregnancy and reduced the rate of preterm birth in women with a singleton and a sonographically short cervix (2). For patients with a cervical length < 25 mm at 20-23 weeks gestation, the pessary reduced the prevalence of preterm birth < 34 weeks from 27% to 6%. Three other cohort studies, 2 retrospective and 1 prospective, provide supportive evidence of prolongation of pregnancy when the pessary is used (1,3,4). One study investigated a particularly high-risk population consisting of twin pregnancies complicated by twin-to-twin transfusion syndrome and a sonographically short cervix. In 2013, a large RCT of 808 multiples (ProTWIN) did not find evidence of benefit in the pessary group. This trial did not require an inclusion criteria of a short cervix, and a significant number of patients in the pessary group either did not receive the pessary (6%) or had the pessary removed prior to 28 weeks (57 patients, 14%). Some of the reasons for removal suggest poor insertion or provider anxiety (lost pessary 7, contractions 5, pain 17). A subgroup analysis suggested that there was benefit for multiple gestations where the cervical length was at the 25th percentile (38mm).

## 1.4 Objectives of the clinical investigation

### 1.4.1 Primary objective

- Frequency of preterm deliveries < 37 weeks 0 days gestation

#### 1.4.2 Secondary Objectives

- Neonatal composite morbidity – fetal or neonatal death, respiratory distress syndrome (RDS), chronic lung disease, periventricular lucency, periventricular leukomalacia, intraventricular hemorrhage grade 3 or 4, necrotizing enterocolitis, early-onset-culture-proven sepsis
- Neonatal length of stay
- Neonatal NICU admission
- Total NICU days
- Duration of ventilator support
- retinopathy of prematurity (ROP) requiring treatment
- birthweight < 1500g and < 2500g
- preterm birth < 34 weeks
- gestational age at delivery
- use of tocolysis
- use of antenatal steroids
- chorioamnionitis
- vaginal bleeding
- preterm premature rupture of membranes
- cesarean delivery

#### 1.5 Anticipated duration of the clinical investigation

KUMC examines approximately 1900 patients in a year for cervical length screening in the 2nd trimester (our standard of care for more than 6 years). Approximately 45 patients a year have cervical lengths < 25 mm.

MUSC examines approximately 2-3 thousand patients per year with cervical length screening. Approximately 60 patients a year have cervical lengths <25 mm.

We expect 80% accrual rate into the study. The expected duration of the study is ~ 4 years.

## 2.0 CLINICAL PROTOCOL

### 2.1 Protocol number

KUOBGYN001: Can the Arabin pessary prevent preterm birth in singleton pregnancies that have a short cervix?

### 2.2 Protocol version number and date

April 24, 2015

## **2.3 Study design**

### **2.3.1 General study design**

This study is a randomized controlled trial. It is not blinded to either investigator or patient.

## **2.4 Subject selection**

### **2.4.1 General characteristics of the proposed subject population(s)**

The patients enrolled into this study are < 23 weeks 0 days pregnant and will have a cervical length < 25 mm detected by transvaginal ultrasound performed during universal screening at each institution participating in this trial. These patients are seeking care at a tertiary care center, and in general have a higher risk profile compared to the community due to presence of maternal disease such as diabetes or hypertension or obstetric history such as prior preterm birth.

The Arabin pessary is designed to reduce preterm birth in pregnant patients with a short cervix. The suggested patients for this clinical trial exactly match the type of patients treated by the Arabin pessary.

### **2.4.2 Anticipated number of research subjects**

We plan to enroll 256 subjects in this study on a 1:1 basis. Our research hypothesis is the proportion of preterm deliveries before 37 weeks 0 days gestation is reduced in the pessary group as compared to the control group. Based on records of patients currently treated for short cervixes here at KUMC and MUSC over the past year, the number of preterm birth before 37 weeks gestation is 30%. In order to detect a reduction in half to 15%, we require a sample size of 242 subjects for analysis. We experience about a 5% loss to follow up rate. We will use an intent-to-treat principle for analyzing the outcomes of the trial. All enrolled patients will provide informed consent for study participation.

### **2.4.3 Inclusion criteria**

- Singleton pregnancy
- Age 18 – 45y
- Cervical length < 25 mm measured by transvaginal ultrasound prior to 23 weeks 0 days
- Agrees to refrain from sexual intercourse

### **2.4.4 Exclusion criteria**

- 
- Major fetal anomalies
- Painful regular uterine contractions
- Active vaginal bleeding
- Ruptured membranes

- Evidence of chorioamnionitis or other serious maternal/fetal infectious morbidity
- Placenta previa
- Current progesterone therapy
- Cervical cerclage in situ
- Visual cervical dilation of 2 cm or greater with visible amnion/chorion
- Significant maternal-fetal complications (insulin dependent diabetes mellitus, systemic lupus erythematosus patients with nephritis, chronic hypertension, red cell alloimmunization, drug abuse)

The PECEP trial (Goya et al 2012) excluded patients with a history of prior cone biopsy. We feel that a history of prior cone biopsy is exactly the type of patient the pessary was designed to treat, a pregnancy at increased risk of preterm delivery due to a shortened cervix. Anatomically, prior cone surgery can lead to a shortened cervix anatomically, which would preclude successful placement of the pessary. Clearly, if a pessary cannot be placed, it will have no effect on outcomes. On the other hand, if the cone surgery has not precluded the placement of the pessary due to anatomy, then we feel that these patients should be included in the study.

Significant maternal-fetal complications are listed as an exclusion since they have increased risk of iatrogenic preterm delivery for reasons that have no relationship with the presence or absence of the pessary. Insulin dependent diabetes with significant proteinuria, lupus patients with nephritis, chronic hypertensives with proteinuria all have increased risks for preeclampsia, intrauterine growth restriction, placental abruption and stillbirth which would impact the outcomes recorded in this study.

## **2.5 Study procedures**

### **2.5.1 Screening procedures**

Patients are identified for the study by universal cervical length screening performed by ultrasound during the 2nd trimester. Once identified, patients are approached by study investigators who are authorized to obtain informed consent. The counseling will take place in the privacy of the ultrasound suite or a private clinic room. Both a medical history and physical exam are performed to verify if a patient meets criteria for enrollment in the study. The physical exam includes a sterile speculum exam which investigates for vaginal or cervical infections in symptomatic patients.

### **2.5.2 Study treatment or diagnostic product procedures**

The treatment proposed in this study is the placement of the Arabin pessary around the cervix. This device currently does not have FDA approval. The company which manufactures the device in Europe has applied for FDA license. A consultant report by NAMSA which describes the device, classification, safety, toxicity, and testing is included in this application.

Patients in the experimental arm will have the Arabin pessary placed at time of enrollment. First, they are assessed for uterine contractions by tocodynamometer. To repeat, if symptoms of genital infection are present, the investigator will perform a sterile speculum exam and a wet mount and cervical cultures for gonorrhea/chlamydia will be obtained. Any symptomatic infections are treated, and the pessary insertion is delayed a week. Any infections resulting after pessary insertion will also be treated. When the pessary is placed, a sterile vaginal examination gel (non-antibiotic) will be used. Once the pessary is placed, patients will return to clinic every 2 weeks for an evaluation. A questionnaire will be filled out for symptoms, and a speculum exam performed to search for infections if the patient is symptomatic. Fetal biometry will be performed monthly, and a transvaginal cervical length will be measured every 2 weeks. The pessary will be removed if there are signs of tissue erosion of the cervix or vagina, intractable pain, or labor. Otherwise, the pessary is removed at 37 weeks.

The control arm will be followed with serial transvaginal ultrasounds to measure cervical length. If the length decreases to less than 20 mm, then vaginal progesterone 200 mg will be prescribed from a local pharmacy. If the cervical length continues to shorten such that membranes are visible at the os, then an emergent cerclage will be offered. Treatments will not be offered after 24 weeks gestation. Similar to the experimental group, patients will return to clinic every 2 weeks for an evaluation. A questionnaire will be filled out for symptoms, and a speculum exam performed to search for infections if the patient is symptomatic. Fetal biometry will be performed monthly, and a transvaginal cervical length will be measured every 2 weeks.

All patients enrolled in the study are seen at the high risk pregnancy clinic at the participating institutions for evaluation. The visit will be recorded in the electronic medical record. The visit will include prenatal care. Results are communicated back to the primary obstetrician by sending a copy of the clinic note back to the inbox of the primary obstetrician.

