### **2.5.6 Procedures to assess efficacy**

Patients are brought back to clinic for evaluation every 2 weeks. They will fill out a questionnaire reviewing their symptoms, fetal biometry will be performed, and the cervical length will be measured by transvaginal ultrasound. A physical exam (including a sterile speculum exam) will search for cervical and vaginal infections if patients are symptomatic. This information is recorded on the web-based case report form (CRF) built and stored by REDCap ([www.project-redcap.org](http://www.project-redcap.org)).

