### **3.3 Withdrawal of subjects due to adverse effects**

Patients are evaluated every 2 weeks for symptoms of pain, abnormal vaginal discharge, and infections. A questionnaire is completed, and a speculum exam to directly assess the cervical and vaginal tissue is performed as needed. Nitrazine, ferning, and pooling will be performed as needed to diagnosed rupture of membranes correctly. The pessary is removed if there are concerning signs of trauma, erosion, intractable pain, and bleeding.

Patients whose pessaries are removed are still analyzed in their assigned group according to an intent-to-treat analysis. Their outcomes and complications are recorded similar to other subjects. They are not replaced.

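### The protocol gives three different lists of reasons for removing the pessary, so active bleeding means removal on some pages and retention on another

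*Combined protocol and SAP*

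**What the plan says.** Four places in the protocol say when the pessary comes out.

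- Synopsis, Safety Evaluations: "Pessaries are removed if there is active vaginal bleeding, risk of preterm labor with persistent contractions, or severe patient discomfort".
- Section 2.5.2: "The pessary will be removed if there are signs of tissue erosion of the cervix or vagina, intractable pain, or labor". The next sentence is "Otherwise, the pessary is removed at 37 weeks".
- Section 3.3: "The pessary is removed if there are concerning signs of trauma, erosion, intractable pain, and bleeding". Section 3.1 has the same sentence, word for word.

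So there are three different lists, one of which appears twice.

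On how such signs would be found, section 2.5.6 says "A physical exam (including a sterile speculum exam) will search for cervical and vaginal infections if patients are symptomatic", and 2.5.7 repeats it. Section 2.5.2 also makes the speculum exam depend on symptoms. Sections 3.1 and 3.3 say that a speculum exam to look directly at the tissue is done as needed. The visit schedule in 2.5.8 marks a physical exam at every visit.

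On analysis, section 3.3 says "Patients whose pessaries are removed are still analyzed in their assigned group according to an intent-to-treat analysis".

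**The concern.** Removal of the device is the main safety action open to an investigator in the pessary arm. The device has no FDA approval (2.5.2), the trial is open-label, and two institutions were to run it. If the lists differ, two investigators can face the same event, follow different pages, and do opposite things while both believe they are following the protocol.

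Compliance checking suffers too. Section 5.0 provides for independent monitoring against the clinical protocol. A monitor who finds a pessary removed for bleeding could call it compliant under 3.3 or a departure from 2.5.2. Vaginal bleeding is a secondary endpoint (1.4.2), so the plan itself expects to record this event.

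**Working it through.** No figure in the plan bears on this point, so the check is a side-by-side reading.

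**Step 1: the lists.**

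| Event | Synopsis | 2.5.2 | 3.1 and 3.3 |
|---|---|---|---|
| Bleeding | Remove (if active) | Not listed | Remove |
| Labor | Not named as such; see next row | Remove | Not listed |
| Persistent contractions with risk of preterm labor | Remove | Not listed | Not listed |
| Tissue erosion | Not listed | Remove | Remove |
| Trauma | Not listed | Not listed | Remove |
| Pain or discomfort | Remove if severe | Remove if intractable | Remove if intractable |

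No reason appears in the same terms in all three columns.

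**Step 2: is any list closed?** A missing reason contradicts another page only if the list that omits it is exhaustive. In 2.5.2 it is: every case not listed goes to removal at 37 weeks. The synopsis and 3.1/3.3 have no such closing sentence, so what they leave out is an omission and not an instruction to keep the device in.

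**Step 3: test cases, all before 37 weeks.** I read each list as needing any one of its signs, although 3.1 and 3.3 join theirs with the word *and*.

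1. Active bleeding, with no erosion, intractable pain or labor. Synopsis: remove. 3.1 and 3.3: remove. 2.5.2: keep until 37 weeks. This is a direct contradiction, three places against one.
2. Persistent contractions judged a risk of preterm labor, labor not established. Synopsis: remove. 2.5.2: keep. 3.1 and 3.3: silent. How sharp the conflict is depends on when labor is held to have begun, which the text does not define.
3. Discomfort that is severe but not intractable. Synopsis: remove. 2.5.2: keep. 3.1 and 3.3: threshold not reached.
4. Trauma without erosion, intractable pain or bleeding. 3.1 and 3.3: remove. 2.5.2: keep, unless trauma is taken to include erosion. Synopsis: silent.
5. Erosion without bleeding or severe discomfort. 2.5.2, 3.1 and 3.3: remove. Synopsis: silent. This is an omission from the synopsis, not a contradiction.

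**Step 4: how the signs are found.** A general physical exam at every visit and a speculum exam only with symptoms can both be carried out, so 2.5.8 and 2.5.6 do not contradict each other. It remains unclear whether a woman without symptoms is ever examined for erosion. The symptom-driven exam in 2.5.6 and 2.5.7 is described as a search for infection, while the exam of the tissue in 3.1 and 3.3 is only as needed.

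**The case against.** The best defense is that sections with different purposes need not repeat each other. The synopsis is a summary, 3.1 is about limiting risk, and 3.3 is about withdrawal for adverse effects, so labor has no natural place in the last two. Some form of pain appears in every list, and erosion is in both body-text lists. Any sensible investigator would also use judgment when a woman bleeds, whatever 2.5.2 says.

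Much of this stands. The absence of labor from 3.1/3.3 and of erosion from the synopsis can be explained in this way, and the other differences leave some room for interpretation. It does not rescue bleeding. Section 2.5.2 is the treatment procedure, it closes its own list, and three other places say the opposite. Reliance on judgment is no answer either, since the written rule is what both sites and the monitor share.

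The examination point is also weaker than it may look. Symptom-driven speculum exams are a stated choice, and 3.1 calls the concern about erosion extremely low. Only the need for clarity survives.

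A reader might also infer that the date and reason of removal go unrecorded. The documents do not support that. Section 9.1 says that the case report forms are attached, they are not in the text available here, and 3.3 says that outcomes and complications are recorded after removal.

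**Conclusion.** The contradiction is real. It is direct for active bleeding, and on the same logic it extends to contractions short of labor, severe but not intractable discomfort, and trauma, with more room for interpretation. It rests on two readings: that the closing sentence of 2.5.2 makes its list exhaustive, and that any one sign is enough in 3.1 and 3.3. Its size is qualitative: a safety event with no single written rule across two sites.

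A reader might infer that the inconsistency dilutes the intent-to-treat effect and costs power. The arithmetic is easily done. The plan's 121 per arm (242 in total), 30% against 15%, with a pooled two-sided z-test at 0.05, gives 80.2% power. Suppose a share *f* of the pessary arm has early removal and returns fully to the control risk, so that the arm's rate is 0.15(1 − *f*) + 0.30*f*. With *f* = 14%, the share that 1.3.1 reports for removal before 28 weeks in a trial of multiple pregnancies, the rate is 0.129 + 0.042 = 17.1% and power is 65.9%.

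The documents do not support attributing that loss to the differing lists:

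- It counts all early removal, which occurs under any list. Only the extra removals caused by the differences would count, and the plan gives no removal rate for this trial.
- One agreed list could raise or lower removals, so reconciling the text would not recover this power.
- The 14% comes from a trial that did not require a short cervix, and bleeding is not among the removal reasons quoted from it.
- Full return to control risk is an assumption. If half the benefit were lost, the rate would be 0.15 + 0.14 × 0.075 = 16.05% and power 73.4%. Removal at labor would change little.
- The 15% is stated for the pessary group in a trial analyzed by intention to treat, and may already allow for removals.

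The cover letter reports seven subjects enrolled and no statistical tests run, so no reported inference is affected. The defect is in the plan and matters for any reuse of it.

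**What to change.** Reconcile the synopsis, 2.5.2, 3.1 and 3.3 into one list of removal reasons. State it once and refer to it from the other places, with one wording for the pain threshold and for contractions or labor, and say plainly whether the list is exhaustive. Which reasons belong on it is for the sponsor to decide.

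In the same edit, say whether the speculum exam that would detect the listed tissue signs is done at every visit or only with symptoms, and bring 2.5.2, 2.5.6, 2.5.7, 3.1 and 3.3 into line with the schedule in 2.5.8.

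The cost is wording in those sections and, in a running trial, the IRB approval that section 8.0 requires for protocol changes. The sample size and the analysis do not change.
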